#### **4.1.4 Definitions of Visit Windows**

Time windows are defined for all summaries of vital signs, ECG, laboratory data, PRO around visits in Section 4.1.4.1 and for tumor assessments around the scheduled RECIST assessment time in Section 4.1.4.2.

##### **4.1.4.1 Visit Windows for Safety and PRO Assessments**

The following conventions will apply for safety and PRO data:

- The time windows should be exhaustive so that data recorded at any time point has the potential to be summarized. Inclusion within the time window should be based on the actual date and not the intended date of the visit.
- All unscheduled visit data will have the potential to be included in the summaries.
- The window for the visits following baseline will be constructed in such a way that the upper limit of the interval falls halfway between the two visits (the lower limit of the first post-baseline visit will be Day 2). If an even number of days exists between two consecutive visits, then the upper limit will be taken as the midpoint value minus 1 day.

For example, the visit windows for vital signs data are:

- Week 1; nominal day 1, visit window Day 1
- Week 4; nominal day 29, visit window 2 – 42
- Week 8; nominal day 57, visit window 43 – 70
- Week 12; nominal day 85, visit window 71 – 98
- Week 16; nominal day 113, visit window 99 – 126
- Visits after treatment discontinuation will be assigned to the last treatment cycle for up to 15 days only. Visits after the 15 days will contribute to the following 30 days post treatment discontinuation interval, see below.
- Visits up to 90 days after last dose will be assigned similarly to the definition for the visits under treatment, but for 30 day intervals after treatment discontinuation, eg,:
  - 30 days after last dose, visit window 16 – 45
  - 60 days after last dose, visit window 46 – 75
  - 90 days after last dose, visit window 76 – 97
  - Data recorded after 97 days after last dose will not contribute to the analysis period of up to 90 days following the date of last dose, and will not be re-mapped
- For summaries showing the maximum or minimum values, the maximum/minimum value recorded on treatment will be used (regardless of where it falls in an interval).
- Listings should display all values contributing to a time point for a patient.

For visit based summaries:

- If there is more than one value per patient within a time window then the closest value to the scheduled visit date should be used, or the earlier in the event the values are equidistant from the nominal visit date. If there are two values recorded on the same day and the parameter is CTCAE gradable then the record with the highest toxicity grade should be used. The listings should highlight the value for that patient that went into the summary table, wherever feasible. Note: in summaries of extreme values all on-treatment values collected are used including those collected at unscheduled visits.
- For summaries at a patient level, all values should be included, regardless of whether they appear in a corresponding visit-based summary, when deriving a patient level statistic such as a maximum.

#### 4.1.4.2 Visit Windows for Tumor Assessments

The following conventions will apply for tumor assessment data:

- All tumor assessments available during the study should be used for the efficacy analysis. A windowing rule will be applied and will follow the CSP allowed visit window; therefore, any RECIST assessment performed within  $\pm 1$  week of the CSP scheduled visit will be used for that visit.

- If there are any assessments outside these visit windows, they will also be included in the closest visit window following the intent-to-treat principle. The tumor assessments which are outside the visit windows will be flagged in the data listings.

The above could result in more than one tumor assessments within a window and in that case, the one closest to the scheduled assessment will be used.

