4.2.2 Rationale for efficacy endpoints

[figure not shown]
The secondary aim of this study is to determine the efficacy of durvalumab 1500 mg q4w in terms of ORR, PFS, and OS. PFS has been found to be correlated with OS in previous CRT studies (Mauguen et al 2013). Although the OS benefit has exceeded the PFS benefit in other studies of immune-checkpoint inhibitors in advanced-stage NSCLC (Borghaei et al 2015), there are certain settings in which the utility of survival as an endpoint may potentially be confounded by subsequent therapies. Specifically, there are currently a number of molecules targeting the

PD-1/PD-L1 pathway in late-stage development for the treatment of first-, second-, and/or third-line metastatic NSCLC. It is anticipated that these agents may be approved or become available for use through expanded-access programs or additional clinical studies while this study is ongoing. This poses challenges in being able to fully characterize effects on OS if patients subsequently receive these immunotherapeutic agents.

Antitumor activity will be assessed according to RECIST 1.1 guidelines, with the understanding that in the context of postradiation changes, tumor assessment may be difficult and may need to be repeated over time to reach a clear determination regarding responses and PD (see Section 8.1). The tumor-based efficacy analyses will be conducted by programmatically deriving each efficacy endpoint based on RECIST 1.1 criteria. PFS will be programmatically derived from Investigators' tumor data from all scans based upon RECIST 1.1.

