### **3. ANALYSIS VARIABLES**

#### **3.1 Derivation of RECIST Visit Responses**

For all patients, the RECIST tumor response data will be used to determine each patient's visit response according to RECIST version 1.1. It will also be used to determine, if and when a patient's disease has progressed in accordance with RECIST and their best objective response to study treatment.

The baseline radiological tumor assessment is part of the screening procedure and should be performed within 28 days after the end of radiotherapy, no more than 28 days before the start of durvalumab treatment, and ideally as close as possible to the start of study treatment. Tumor assessments will begin at 8 weeks  $\pm$  1 week after durvalumab initiation and continue every 8 weeks  $\pm$  1 week through 48 weeks (relative to the date of first dose of durvalumab), and then every 12 weeks  $\pm$  1 week thereafter until RECIST 1.1-defined PD, plus an additional regularly scheduled follow-up scan. The on-study schedule of q8w  $\pm$  1 week (following the first assessment at 8 weeks  $\pm$  1w after the first dose) for first 48 weeks and then q12w  $\pm$  1 w thereafter MUST be followed regardless of any delays in dosing. Additional scans can be completed per standard practice post disease progression.

From the investigator's review of the imaging scans, the RECIST tumor response data will be used to determine each patient's visit response according to RECIST version 1.1. At each visit, patients will be programmatically assigned a RECIST 1.1 visit response of CR, PR, SD or PD, using the information from target lesions (TLs), non-target lesions (NTLs) and new lesions and depending on the status of their disease compared with baseline and previous assessments. If a patient has had a tumor assessment which cannot be evaluated, then the patient will be assigned a visit response of not evaluable (NE) (unless there is evidence of progression in which case the response will be assigned as PD).

RECIST outcomes (ie, PFS and ORR etc.) will be calculated programmatically from site investigator data from overall visit responses.

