### **3.3 Efficacy Variables**

All RECIST assessments, whether scheduled or unscheduled, and regardless of whether a patient discontinues durvalumab treatment or receives another anti-cancer therapy will be included in the calculation of efficacy variables.

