- The data will be included in summaries/analyses using the following criteria:
  - All laboratory data, vital signs and ECG data that are recorded at unscheduled visits will be included in the summaries using the visit windows defined in Section 4.1.4.1.
  - The tumor measurements and PRO data should not be affected by any delays in treatment cycles/dates of start of treatment cycles as it is intended that they are only recorded at pre-scheduled time points. These data will be included in the summaries and analyses of the data using the visit windows defined in Section 4.1.4.2.
- All data collected including scheduled, delayed and unscheduled data will be listed in the patient data listings which are produced for all treated patients. They will be ordered by treatment/not treated, centre, radiotherapy group, patient and visit and, if relevant, timepoint when they were recorded. Patients who are included in the SAF will be flagged. Depending on the availability of the data, all data for the patients who are not treated will be listed separately. They will be ordered by centre, radiotherapy group, patient and visit and timepoint, if relevant.
- All adverse events will be coded using MedDRA and NCI CTCAE Grade and will be reported using SOC and PT, and NCI CTCAE Grade, as appropriate.
- All concomitant and previous medications will be coded using WHO drug dictionary and will be reported using anatomical therapeutic chemical (ATC) classification and generic term.
- Baseline is defined as the last assessment of the variable under consideration prior to the first dose of durvalumab regardless of whether the assessment is on Day 1, Screening or unscheduled.
- Patients who failed the screening in the first instance but later rescreened and passed the screening will be part of summary tables along with other patients who passed the screening in the first instance.
- Patients who failed both first screening and rescreening will not be part of summary tables but a listing will be generated for these patients.

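### The closest-scan rule in SAP 4.1.4.2 conflicts with the all-scans rule for efficacy and, if applied to the endpoints, can delay or drop a progression event

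*SAP*

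**What the plan says.** Three places call for every scan to count:

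- SAP 3.3 (Efficacy Variables) puts into the efficacy calculations "All RECIST assessments, whether scheduled or unscheduled".
- Protocol 4.2.2 derives PFS from the Investigators' "tumor data from all scans based upon RECIST 1.1".
- SAP 4.1.4.2 opens: "All tumor assessments available during the study should be used for the efficacy analysis".

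The rest of SAP 4.1.4.2 then selects among scans. A scan within ±1 week of a scheduled visit belongs to that visit. For scans outside those windows, "they will also be included in the closest visit window following the intent-to-treat principle". If a window then holds more than one scan, "in that case, the one closest to the scheduled assessment will be used". The section has no exception for PD and no rule for ties.

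Two places connect this selection to the endpoints. SAP 4.1.1 says of the tumour and PRO data: "These data will be included in the summaries and analyses of the data using the visit windows defined in Section 4.1.4.2". SAP 3.1 says: "RECIST outcomes (ie, PFS and ORR etc.) will be calculated programmatically from site investigator data from overall visit responses".

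Two places point the other way. SAP 4.1.4 introduces the time windows in terms of summaries, and SAP 3.3.1 defines PFS, its censoring and its missed-visit limits from assessment dates without mentioning windows.

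**The concern.** A program cannot both use every scan and keep one scan per window. The SAP does not say which instruction governs the endpoints. A programmer who takes SAP 4.1.1 and 3.1 at their word would choose one scan per visit, assign the visit response from it, and derive PFS from those responses. PD on an unscheduled scan would then disappear whenever another scan in the same window lies nearer to the nominal date.

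PFS, PFS6 and PFS12 are at stake, together with DoR, whose end date SAP 3.3.5 takes from PFS. ORR and BoR rest on the same visit responses. SAP 3.3.3 requires that no progression occur between a response and its confirmation, so a dropped PD could also leave a response counted as confirmed.

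The situation is foreseeable. The protocol (Table 1 footnotes, 7.1.3 and Appendix F) asks for a follow-up scan after a first PD, at least 4 weeks later and no later than the next scheduled imaging visit. Protocol 4.2.2 also expects some assessments to be repeated because post-radiation changes are hard to read.

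**Working it through.** **Inputs.** Scans are 8-weekly to Week 48, then 12-weekly, each ±1 week (Protocol Table 1; SAP 3.1). Landmarks are Day 180 for PFS6 and Day 365 for PFS12 (SAP 4.4.1). Missed-visit limits are in SAP 3.3.1. About 102 patients are treated (SAP 1.2).

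**The plan's own figures.** The limits reproduce: 2×8+1 = 17, 2×8+1+1 = 18, 2×10+1+1 = 22 and 2×12+1+1 = 26 weeks. Week *w* is day 7*w*+1, so Week 39 is day 274 and Week 49 is day 344, as stated. Scheduled scans therefore fall on days 57, 113, 169, 225, 281 and 337, then 421, 505 and so on.

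**When the required follow-up scan displaces the PD scan.** The midpoint of days 57 and 113 is 85, so a PD scan joins the Week 16 window from day 86. The follow-up must be at least 28 days later and by day 113+7 = 120, so the PD lies on days 86 to 92, which is 7 of the 56 days between visits. The PD scan is then 21 to 27 days from day 113 and the follow-up 1 to 7 days, so the PD scan is always the one dropped. Protocol 6.1.3 and 8.1 instead time the follow-up at 4–8 weeks. On that text, with PD on day *p* and follow-up at the earliest on day *p*+28, the follow-up is nearer when (*p*+28)−113 < 113−*p*, that is *p* < 99.

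**Constructed scan histories** (illustrations, not trial data), derived both ways:

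| History | All scans (SAP 3.3) | One scan per window (SAP 4.1.4.2) |
|---|---|---|
| A: SD day 57, PD day 92, PD day 120 | event day 92 | event day 120 (120−92 = 28 days later) |
| B: SD day 57, PD day 92, SD days 120 and 169 | event day 92 | censored day 169 |
| C: SD days 57 and 113, PD day 127, no later scan, death day 260 | event day 127 | censored day 113 |
| D: SD to day 169, PD day 176, PD day 225 | event day 176 | event day 225 (49 days later; crosses Day 180) |
| E: SD to day 337, PD day 358, PD day 421 | event day 358 | event day 421 (63 days later; crosses Day 365) |

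In C, once the PD scan is dropped, the death comes (260−113)/7 = 21 weeks after the last retained scan. That exceeds the 18-week limit, so the death is not counted either.

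**Largest delay when the dropped PD precedes the retained scan,** with the retained scan inside its ±1-week window: half the interval plus one week. This is 28+7 = 35 days on the 8-weekly schedule and 42+7 = 49 days on the 12-weekly schedule. Both put the PD exactly at the midpoint between visits, where the SAP has no tie rule; one day inside the window gives 34 and 48. When the dropped PD follows an on-time scan, as in D and E, the delay can be longer.

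**Per-patient effect.** Ignoring earlier censoring, one patient moved across a landmark changes PFS6 or PFS12 by 1/102 = 0.98 percentage points. The documents give no rate of unscheduled scans. On an assumed 2 to 10 such patients the change would be 2/102 = 2.0 to 10/102 = 9.8 points; that range is an assumption, not an estimate.

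**The case against.** The strongest reply is that the windows are for display only. The first sentence of SAP 4.1.4.2, SAP 3.3 and Protocol 4.2.2 all say every scan counts. SAP 3.3.1 works from dates, SAP 3.3.4 accepts a response at any time after Day 1 and before progression or further therapy, and SAP 4.1.4 speaks of summaries. The sentence in SAP 4.1.1 is a loose cross-reference: it sends PRO data to 4.1.4.2, although PRO windows are in 4.1.4.1. On this reading no PFS event moves.

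This reading is tenable, so a reader should not infer that the plan definitely discards progression scans. The text does not secure it, however. SAP 4.1.1 says analyses, and SAP 3.1 derives the endpoints from visit responses. The safety and PRO windows in 4.1.4.1 place their closest-value rule under visit-based summaries and exempt patient-level statistics; the tumour section does neither. In the unredacted text, SAP 4.4 contains no by-visit tumour table; SAP 3.1.1.2 mentions only a listing of visit responses.

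Three tempting extensions fail:

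- PD at Week 13 with a scan at Week 16 looks like a natural example, but a follow-up after 3 weeks breaks the protocol's 4-week minimum. Day 92 with day 120 complies.
- Half the scan interval (4 or 6 weeks) looks like the maximum delay, but it leaves out the one-week tolerance on the retained scan.
- Appendix F might be read as requiring an unconfirmed first PD to stand in the analysis. It tells the Investigator not to revise that assessment; it is not a derivation rule.

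**Conclusion.** The concern holds as a conflict in the text with a conditional consequence. SAP 4.1.4.2 contradicts itself, SAP 3.3 and Protocol 4.2.2, and the SAP leaves open whether the closest-scan rule reaches the endpoints.

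Harm requires three things together: the rule is applied to the endpoints, two scans share a window, and the PD scan is the one further from schedule. A dropped PD then either moves the event later or removes it, so its effect on PFS, PFS6, PFS12 and the end of response in DoR favours the drug. It would be tempting to conclude that these results are biased. The documents support only that they could be, by an unknown amount. The effect on ORR and BoR need not run one way, because a dropped response scan could also cost a patient a confirmed response.

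All these endpoints are secondary and descriptive in a single-arm study. The primary endpoint, Grade 3 and 4 possibly related adverse events, and the sample size are unaffected. The point should still be corrected, because two careful programmers could obtain different PFS results from the same data.

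**What to change.** Make these changes to the SAP:

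1. In 4.1.4.2, limit the closest-scan rule to by-visit displays and listings.
2. State that PFS, ORR, BoR and DoR use every RECIST assessment on its actual date, and that the earliest RECIST 1.1 PD, on a scheduled or unscheduled scan, is the progression event. The existing missed-visit and subsequent-therapy rules continue to apply.
3. Align the sentence in 4.1.1 with this.

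The cost is two sentences plus the cross-reference. No data collection changes, and the result is what SAP 3.3 and Protocol 4.2.2 already describe. If endpoint programs already exist, check that none selects one scan per window before deriving PFS.

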## **4.2 Study Population**

### **4.2.1 Patient Disposition**

The following patient disposition summaries will be produced:

- The number and percentage of patients who were screened, who were screening failures, and who received and did not receive durvalumab will be summarised for all patients.
- Discontinuation from durvalumab and/or discontinuation from study, together with reason for discontinuation (including the reason due to COVID-19 Pandemic) will be summarised using the SAF.
- Disruptions due to COVID-19
- Summary of confirmed/suspected COVID-19 infection.

The date of the last contact (date of withdrew consent/lost to follow-up/died) will be listed in patient disposition listings. COVID-19 study disruptions will also be listed along with issues reported in the Clinical Trial Management System.

### **4.2.2 Protocol Deviations**

Important protocol deviations are defined in Section [2.2](#) and will be listed and summarized for the SAF.

The number and percentage of patients with any IPD will be summarized for each IPD category. Patients with more than one deviation in the same IPD category will be counted once for that IPD category. Any patients who have deviations in more than one IPD category will be counted once in the overall summary. The number of patients with at least 1 COVID-19 related important protocol deviation and the number of patients with at least 1 important protocol deviation, excluding COVID-19 will be presented by IPD category.

### **4.2.3 Demography and Baseline Characteristics**

Demographic and other baseline characteristics (see Section [3.5.1](#)) will be listed for all patients and summarised for the SAF, as:

- Demographics (age (years), age group [ $<50$ ,  $\geq 50$ - $< 65$ ,  $\geq 65$ - $< 75$ , and  $\geq 75$  years], sex, race and ethnicity)
- Demographic characteristics in patients with confirmed/suspected COVID-19 infection.

- Patient characteristics at baseline (height (cm), weight (kg) [prior to start of radiotherapy, and after radiotherapy at screening, and the change], weight groups [ $<40$ ,  $\geq 40$ - $< 75$ ,  $\geq 75$ - $<90$ ,  $\geq 90$ - $<120$ , and  $\geq 120$  kg], body mass index (BMI kg/m^2) after radiotherapy, and BMI groups [Underweight ( $<18.5$ ), Normal weight ( $\geq 18.5$  -  $<25.0$ ), Overweight ( $\geq 25.0$  -  $<30.0$ ), Obese ( $\geq 30.0$ ) kg/m^2]
- Nicotine use and consumption
- A summary and a list of patients by site and country will be provided.
- Previous disease-related radiotherapy and cancer therapy.
- Disease characteristics (CCl [REDACTED], AJCC staging at baseline and diagnosis, histology type at diagnosis, TNM classification at diagnosis, tumor location and time from diagnosis to first dose
- Extent of disease (Radiological assessment, site of locally advanced disease, recurrence of earlier cancer, NSCLC progressing at study entry, time from most recent progression to study entry, reason tumor not amenable for resection
- Medical history in patients with confirmed/suspected COVID-19 infection.

Medical history and relevant surgical history are coded using MedDRA and will be summarized by SOC and PT.

#### **4.2.4 Previous and Concomitant Medications and Procedures**

Prior and concomitant medications and procedures will be listed for all patients in the SAF.

Concomitant medications and procedures will be summarized by therapeutic subgroup (ATC 2nd level), chemical subgroup (ATC 4th level), and preferred WHO name for the SAF. Patients with the same concomitant medication/procedure multiple times will be counted once per medication/procedure. A medication/procedure that can be classified into more than one chemical and/or therapeutic subgroups will be presented in each subgroup.

#### **4.2.5 Study Drug Administration**

Individual patient data for study drug administration will be listed for all patients in the SAF.

### **4.3 Analysis of Primary Safety Endpoint**

The primary endpoint of this study is the incidence of Grade 3 and Grade 4 PRAEs (see Section 3.2.3.1) which occur within the first six months (ie, up to and including the 183rd day) after the initiation of durvalumab. Any Grade 3 or Grade 4 PRAEs which started after the 183rd day of the study, or after the 90th day following discontinuation of durvalumab, or after the start of subsequent anti-cancer therapy will not be included.

The number and percentage (and exact Clopper-Pearson 95% CI) of patients with NCI CTCAE Grade 3 or Grade 4 PRAEs, both overall and for those occurring within the first six months after initiation, will be summarized for the SAF for all patients and within the standard and palliative radiotherapy cohorts. This summary will also be graphically presented as a bar chart. The

number and percentages of patients with NCI CTCAE Grade 3 or Grade 4 PRAEs will also be summarized by SOC and PT.

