9.5.1 Analysis of the primary variable

Safety data will be summarized descriptively overall, by seriousness, by causality, and by maximum NCI CTCAE Grade. The exact 95% CIs around the incidence of Grade 3 and Grade 4 PRAEs will be reported for patients overall and separately for each cohort.

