#### 2.1.1 Safety Analysis Set

The Safety Analysis Set: will consist of all patients who received at least one dose (partial or in full) of durvalumab. The SAF will be used for analysis of all safety endpoints. In this safety study, the standard full analysis set will be same as SAF, therefore, the SAF will be used for analysis of efficacy endpoints as well.

For analysis of time-to-event endpoints, the SAF will be used with defined censored patients.

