### 3.2.1 Primary Safety Endpoint

The primary endpoint of this study is the incidence of Grade 3 and Grade 4 PRAEs (see Section 3.2.3.1) which occur within the first six months (ie, up to and including the 183rd day) after the initiation of durvalumab. Any Grade 3 or Grade 4 PRAEs which started after the 183rd day of the study, or after the 90th day following discontinuation of durvalumab, or after the start of subsequent anti-cancer therapy will not be included.

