### **3.2.3 Adverse Events**

AEs and SAEs will be collected throughout the study, from time of the patient signing the informed consent and 90 days after the last dose of durvalumab. A treatment emergent adverse event (TEAE) is an AE with an onset date or a pre-existing AE worsening following the first dose of study treatment through to 90 days after the last dose of durvalumab.

The Medical Dictionary for Regulatory Activities (MedDRA) (using the latest or current MedDRA version) will be used to code the AEs. AEs will be graded according to the National Cancer Institute Common Terminology Criteria for AEs (CTCAE Version 5.0). The meaning of these categories are as follows:

- Grade 1: Mild AE
- Grade 2: Moderate AE
- Grade 3: Severe AE
- Grade 4: Life-threatening or disabling AE
- Grade 5: Death related to AE

Any TEAE will be included in the AE summaries as detailed in Section 4.5.1.

Missing start and stop dates for AEs will be imputed using the rules described in Section 4.1.3.

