#### **3.2.3.1 Possibly-Related Adverse Events**

A PRAE is any TEAE with a relatedness to durvalumab of possible, or where the relatedness is missing. When the relatedness of a TEAE is missing on the electronic Case Report Form (eCRF), all efforts will be taken to ensure that the Investigator assigns his/her assessment of relatedness prior to DBL.

If relatedness of a TEAE is missing at the DBL, as given in Section 4.1.2, the TEAE will be considered as possibly related to durvalumab.

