  - This summary will include an AE event rate (per 100 patient years) for each PT. The number of patients with an AE in each PT is divided by the sum of the actual exposure to durvalumab (days) (see Section 0) over all patients. This is multiplied by 365.25 x 100 to create an event rate per 100 patient years.
- All AEs by maximum CTCAE Grade
- All AEs / PRAEs with outcome of death
- All SAEs / Serious PRAEs
- All AEs / PRAEs leading to discontinuation from durvalumab (Note: Reason for discontinuation recorded on the patient disposition page)
- All AEs / PRAEs leading to dose interruption/discontinuation of durvalumab (Note: Reason for discontinuation recorded on the patient disposition page)

A summary of most common AEs and another summary of most common AEs with CTCAE Grade 3 or higher, including all events that occur in at least 2.5% of patients overall will be presented by PT, by decreasing frequency. This cut-off may be modified after review of the data. The raw percentage will be compared to the cut-off, without applying any rounding to the percentage value (ie, a TEAE with frequency of 2.4% will not appear in the table if a cut-off is 2.5%).

A summary of deaths will be provided with the following information:

- Number of deaths (NSCLC-related, non-related, and unknown)
  - Number of deaths during the on-treatment study period up until 90-day follow-up

- and prior to initiation of first subsequent therapy
- Number of deaths occurring more than 90 days after the discontinuation of durvalumab or after initiation of first subsequent therapy

Listings of key patient information for Deaths and SAEs will be provided.

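### The headline six-month toxicity rate stops at Grade 4, so a patient whose only severe related event is fatal counts as a non-event, and no planned summary gives the Grade 3 to 5 rate

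*SAP*

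**What the plan says.** SAP 3.2.1 states: "The primary endpoint of this study is the incidence of Grade 3 and Grade 4 PRAEs". SAP 4.3 repeats the definition, limits it to events "which occur within the first six months (ie, up to and including the 183"rd day), and gives the statistic as "The number and percentage (and exact Clopper-Pearson 95% CI) of patients with NCI CTCAE Grade 3 or Grade 4 PRAEs", for all patients and within each radiotherapy cohort. Protocol 9.5.1 agrees: "The exact 95% CIs around the incidence of Grade 3 and Grade 4 PRAEs will be reported for patients overall and separately for each cohort".

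Three other definitions decide who is counted:

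- The severity scale in SAP 3.2.3 has a fifth category: "Grade 5: Death related to AE".
- SAP 3.2.3.1 puts no grade limit on relatedness: "A PRAE is any TEAE with a relatedness to durvalumab of possible, or where the relatedness is missing". A fatal related event is therefore a PRAE.
- The denominator is the Safety Analysis Set of SAP 2.1.1, which "will consist of all patients who received at least one dose (partial or in full) of durvalumab".

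SAP 4.5.1 reports fatal PRAEs as a row of the overall adverse event summary and in a table by system organ class and preferred term. It also plans "another summary of most common AEs with CTCAE Grade 3 or higher".

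**The concern.** The primary numerator covers two of the three severe categories on the scale. The one left out is the worst, and the patients in it stay in the denominator. Other things equal, the headline rate falls when a patient's only severe related event is fatal instead of Grade 4.

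This matters because safety is the primary objective of this single-arm trial, in patients judged unfit for chemotherapy and with performance status up to 2. Protocol 4.2.1 justifies the study partly by the possibility that radiotherapy raises the risk of pneumonitis with this drug class, which can be fatal. The six-month percentage with its interval is the figure most readers will take away.

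A second question is how an event that worsens is counted. Protocol 8.3.4 collects both the maximum grade and changes in grade. SAP 4.3 does not say whether any recorded Grade 3 or 4 is enough or whether the maximum grade must be 3 or 4. Under the second rule, a Grade 3 pneumonitis that becomes fatal leaves the numerator.

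**Working it through.** **Step 1: the plan's own figures.** The exact (Clopper-Pearson) limits for x events in n patients are: lower = 2.5% quantile of Beta(x, n − x + 1); upper = 97.5% quantile of Beta(x + 1, n − x). With n = 60 and 12% (x = 7.2, a non-integer count that the planning table implies), the limits are 5.0 to 23.0. With n = 30 and 12% (x = 3.6) they are 3.1 to 29.1. Both match Protocol Table 11 and SAP Table 1. The stated precision is not in question.

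**Step 2: who is in the numerator.** Take a treated patient with at least one PRAE of Grade 3 or worse starting by Day 183.

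- Some PRAE is Grade 3 or 4, with or without a separate Grade 5 event: counted.
- The only such PRAE is Grade 5 from the outset: not counted.
- The only such PRAE went from Grade 3 or 4 to Grade 5: counted if any recorded grade qualifies, not counted if maximum grade is used. SAP 4.3 does not say which.

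**Step 3: whether another summary fills the gap.**

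- PRAEs with a fatal outcome (SAP 4.5.1): no Day 183 limit and no exact interval. Their patients may overlap with the Grade 3/4 patients, so the two counts cannot be added.
- Six-month PRAE table by organ class and preferred term (SAP 4.5.1): again Grade 3 or 4 only.
- All events by maximum grade, and the common-event table that includes Grade 5 (SAP 4.5.1): all causes, no six-month window.
- Deaths summary (SAP 4.5.1): split by relation to the lung cancer, not to the drug.

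None gives the six-month proportion of patients with a Grade 3, 4 or 5 PRAE.

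**Step 4: size.** The planned numbers treated are 102 in all, 59 standard and 43 palliative (SAP 1.3). One uncounted patient lowers the rate by 1/102 = 1.0 point, 1/59 = 1.7 points or 1/43 = 2.3 points.

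For illustration, start from the whole number nearest to the 12% planning rate: 0.12 × 102 = 12.2, so 12; 0.12 × 59 = 7.1, so 7; 0.12 × 43 = 5.2, so 5. Then add g uncounted patients. The documents give no value for g, so 0 to 3 is an assumed range.

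| g | All (n = 102) | Standard (n = 59) | Palliative (n = 43) |
|---|---|---|---|
| 0 | 12: 11.8% (6.2 to 19.6) | 7: 11.9% (4.9 to 22.9) | 5: 11.6% (3.9 to 25.1) |
| 1 | 13: 12.7% (7.0 to 20.8) | 8: 13.6% (6.0 to 25.0) | 6: 14.0% (5.3 to 27.9) |
| 2 | 14: 13.7% (7.7 to 22.0) | 9: 15.3% (7.2 to 27.0) | 7: 16.3% (6.8 to 30.7) |
| 3 | 15: 14.7% (8.5 to 23.1) | 10: 16.9% (8.4 to 29.0) | 8: 18.6% (8.4 to 33.4) |

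Each column stands alone; g is the number in that group. In the first column, the half-width of the interval goes from 6.7 points at g = 0 to 7.3 at g = 3, so counting Grade 5 costs almost no precision.

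**The case against.** The strongest reply is that this is a deliberate endpoint, defined the same way throughout both documents, and that nothing is concealed. Fatal PRAEs appear in the same overall summary as the Grade 3/4 row, and again in their own table. SAP 4.1.1 requires safety data by cohort as well as overall. The planned listings carry onset date, relatedness and grade, so the missing rate could be rebuilt by hand. The analysis is descriptive, with no test or threshold, so no pre-specified decision turns on a point or two.

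Most of that stands. The point is not a contradiction or a wrong figure, and a reader who inferred that deaths are hidden would be mistaken. What remains is that the combined rate, its window and its interval are in no planned summary.

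Four stronger readings are tempting, and the documents do not support them:

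- *Every fatal PRAE is lost from the primary count.* A patient with another Grade 3 or 4 PRAE in the window is still counted. Loss of an event that worsens depends on a rule the SAP leaves unstated. SAP 4.5.1.1 names maximum grade for events of special interest; SAP 4.3 does not.
- *The understatement is largest in the palliative cohort.* That 1/43 exceeds 1/59 shows only that one patient weighs more in a smaller group. The expected understatement is the probability that a patient would be left out in this way, and nothing in the documents says this is higher in that cohort.
- *The tolerability conclusion should rest on the Grade 3 to 5 rate.* That would replace, through the SAP, the primary endpoint the protocol defines.
- *The Grade 3 or higher cut-off in the common-event table shows the SAP contradicting itself.* That table covers all causes with no six-month limit, and serves a different purpose.

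**Conclusion.** The concern holds in a limited form. Under the definitions in SAP 3.2.1 and 4.3 and Protocol 9.5.1, a patient whose only Grade 3-or-worse PRAE by Day 183 is Grade 5 counts as a non-event. A patient whose only such event worsened from Grade 3 or 4 to Grade 5 may also be missed, depending on an unstated rule. The effect on the rate can only be downward. With an assumed three such patients, the overall figure would read 11.8% where the Grade 3 to 5 rate is 14.7%, and the intervals overlap heavily. The true number could be zero, in which case the two rates are identical.

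The documents do not say whether the 12% planning figure from the earlier durvalumab trial includes Grade 5 events. That is a further reason to keep the Grade 3/4 rate and show the wider one beside it. Rating: a cheap improvement, not an error that invalidates the analysis.

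**What to change.** Keep the Grade 3/4 primary endpoint as it is. In SAP 4.3:

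1. Add, directly beside the six-month Grade 3/4 row, a supporting row with the number, percentage and exact Clopper-Pearson 95% interval of patients with a Grade 3, 4 or 5 PRAE within 183 days, overall and by cohort.
2. State that an event reaching Grade 5 after a recorded Grade 3 or 4 within the window still counts in the Grade 3/4 numerator.
3. State that the two rates will be presented together wherever tolerability is described.

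The data are already collected, including grade changes. The cost is one table row, a few lines of SAP text and a possibly slightly less favourable figure. The change should be made before database lock. If lock has already passed, which the documents do not show, the row should be labelled as added afterwards.
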